#### **Pregnancy**

#### Maternal exposure

If a patient becomes pregnant during the course of the study, the IPs should be discontinued immediately.

Pregnancy itself is not regarded as an AE unless there is a suspicion that the IP under study may have interfered with the effectiveness of a contraceptive medication. Congenital abnormalities or birth defects and spontaneous miscarriages should be reported and handled as SAEs. Elective abortions without complications should not be handled as AEs. The outcome of all pregnancies (spontaneous miscarriage, elective termination, ectopic pregnancy, normal birth, or congenital abnormality) should be followed up and documented even if the patient was discontinued from the study.

If any pregnancy occurs in the course of the study, then the Investigator or other site personnel should inform the appropriate AstraZeneca representatives within 1 day, i.e., immediately, but no later than 24 hours of when he or she becomes aware of it.

The designated AstraZeneca representative will work with the Investigator to ensure that all relevant information is provided to the AstraZeneca Patient Safety data entry site within 1 to 5 calendar days for SAEs and within 30 days for all other pregnancies.

The same timelines apply when outcome information is available.

#### Paternal exposure

Male patients should refrain from fathering a child or donating sperm during the study and for 180 days after the last dose of durvalumab + any drug combination therapy or 90 days after the last dose of durvalumab monotherapy, whichever is the longer time period. Pregnancy of the patient's partner is not considered to be an AE. However, the outcome of all pregnancies (spontaneous miscarriage, elective termination, ectopic pregnancy, normal birth, or congenital abnormality) occurring from the date of the first dose until 180 days after the last dose of durvalumab + any drug combination therapy or 90 days after the last dose of durvalumab monotherapy, whichever is the longer time period should, if possible, be followed up and documented.

Where a report of pregnancy is received, prior to obtaining information about the pregnancy, the Investigator must obtain the consent of the patient's partner. Therefore, the local study team should adopt the generic ICF template in line with local procedures and submit it to the relevant Ethics Committees (ECs)/Institutional Review Boards (IRBs) prior to use.

#### 8.0 DRUG/TREATMENT INFORMATION

#### 8.1 Durvalumab

- Other names for the drug(s): MEDI 4736, IMFINZI
- Classification type of agent: Immunotherapy
- Mode of action: PD-L1 blockage
- Protocol dose: Durvalumab/MEDI 4736 is administered 1500mg every 4 weeks (28±3 days) [Q4W] intravenous during concurrent radiotherapy, 1500mg every 4 weeks [Q4W] (28±3 days) intravenous [iv] up to one year during consolidative phase. Durvalumab/MEDI 4736 will be started within ± 3 days of the start date of radiation therapy.
- Formulation/packaging/storage: Durvalumab (MEDI4736) will be supplied by AstraZeneca as a 500-mg vial solution for infusion after dilution. The solution contains 50 mg/mL durvalumab (MEDI4736), 26 mM histidine/histidine hydrochloride, 275 mM trehalose dihydrate, and 0.02% weight/volume (w/v) polysorbate 80; it has a pH of 6.0 and density of 1.054 g/mL. The nominal fill volume is 10.0 mL. Investigational product vials are stored at 2°C to 8°C (36°F to 46°F) and must not be frozen. Drug product should be kept in original packaging until use to prevent prolonged light exposure.
- Preparation of durvalumab doses for administration with an IV bag: The dose of durvalumab (MEDI4736) for administration must be prepared by the Investigator's or site's designated IP manager using aseptic technique. Total time from needle puncture of the durvalumab (MEDI4736) vial to the start of administration should not exceed:
  - 24 hours at 2°C to 8°C (36°F to 46°F)
  - 4 hours at room temperature
- A dose of 1500mg (for patients >30kg in weight) will be administered using an IV bag containing 0.9% (w/v) saline or 5% (w/v) dextrose, with a final durvalumab concentration ranging from 1 to 15 mg/mL, and delivered through an IV administration set with a 0.2- or 0.22-μm filter. Add 30.0 mL of durvalumab (ie, 1500mg of durvalumab to the IV bag. The IV bag size should be selected such that the final concentration is within 1 to 15 mg/mL. Mix the bag by gently inverting to ensure homogeneity of the dose in the bag.
- If weight falls to ≤ 30 kg, weight-based dosing at 20 mg/kg will be a administered using an IV bag containing 0.9% (w/v) saline or 5% (w/v) dextrose, with a final durvalumab concentration ranging from 1 to 15mg/mL, and delivered through an IV administration set with a 0.2- or 0.22-µm filter.
- Standard infusion time 1 hour. In the event that there are interruptions during infusion, the total allowed infusion time should not exceed 8 hours at room temperature.
- Do not co-administer other drugs through the same infusion line.
   The IV line will be flushed with a volume of IV diluent equal to the priming volume of the infusion set used after the contents of the IV bag are fully administered, or complete the infusion according to institutional policy to ensure the full dose is administered. If

either preparation time or infusion time exceeds the time limits a new dose must be prepared from new vials. Durvalumab does not contain preservatives, and any unused portion must be discarded.

- Side effects: Durvalumab can cause serious, potentially fatal adverse reactions including immune-mediated pneumonitis, hepatitis, colitis or diarrhea, endocrinopathies, nephritis, rash or dermatitis, other immune-mediated adverse reactions, infection, and infusion-related reactions. Refer the reader to the agent's package insert for a comprehensive list of adverse events.
- Monitoring of dose administration: Patients will be monitored during and after the infusion with assessment of vital signs at the times specified in the Study Protocol.
- In the event of a ≤Grade 2 infusion-related reaction, the infusion rate of study drug may be decreased by 50% or interrupted until resolution of the event and re-initiated at 50% of the initial rate until completion of the infusion. For patients with a ≤Grade 2 infusion-related reaction, subsequent infusions may be administered at 50% of the initial rate. Acetaminophen and/or an antihistamine (e.g., diphenhydramine) or equivalent medications per institutional standard may be administered at the discretion of the investigator. If the infusion-related reaction is ≥Grade 3 or higher in severity, study drug will be discontinued. For management of patients who experience an infusion reaction, please refer to the toxicity and management guidelines in Appendix 1.
- As with any antibody, allergic reactions to dose administration are possible. Appropriate drugs and medical equipment to treat acute anaphylactic reactions must be immediately available, and study personnel must be trained to recognize and treat anaphylaxis. The study site must have immediate access to emergency resuscitation teams and equipment in addition to the ability to admit patients to an intensive care unit if necessary

#### 8.1.1 Return and Retention of Study Drug

Remaining drug will be destroyed according to institutional pharmacy instructions.

#### 9.0 CORRELATIVES/SPECIAL STUDIES

The goal of the planned laboratory correlative studies is to understand the effect of tumor PD-L1 expression on treatment response to anti-PD-L1 targeted immunotherapy

#### 9.1 Sample Collection Guidelines

In this study, it is recommended that tissue be submitted to pathology department at UT Southwestern for PD-L1 expression analysis for all patients. It is highly recommended (but optional for the patient) that if any tissue remains after analysis, it will be stored at the Tissue Bank at UT Southwestern for future research. In addition, it is highly recommended (but optional for the patient) that fresh-frozen tumor biopsy, serum and peripheral blood specimens be submitted for the additional tests,

Optional Samples will be collected at the following time points (+/- 7 days):

- Tissue submission to pathology department at UT Southwestern for PD-L1 expression analysis for all patients (within 28 days) prior to study treatment.
- Collection of 8cc plasma at study enrollment, at week 6, week 12 and end of the study.

#### 9.2 Assay Methodology

PDL-1 testing will utilize the Ventana SP263 assay and should be performed in accordance with the package insert on the Ventana Benchmark platform (Ultra or XT). The remaining tumor samples may be used to analyze the expression and spatial distribution of immune-related or response-related markers by multiplex immunohistochemistry, which may

include but are not limited to PD-L1, CTLA-4, CD3, CD4, CD8, CD45RO, FOXP3, granzyme B, OX40, PD1, cleaved caspase 3, and Ki67. Archived material (or biopsies if available) may also be analyzed for the presence of key genomic features such as EGFR, KRAS, and ALK alterations to evaluate their potential relevance and correlations with response to durvalumab. Blood samples will be analyzed to evaluate protein, nucleic acid, and cellular biomarkers that relate to durvalumab. PBMC will also be isolated from whole blood and will be preserved, and may be used for subsequent flow cytometry or assessment of the diversity of the immune cell repertoire based on VDJ coding region analysis, the relationship to clinical responses, and changes in response to treatment with durvalumab. Blood collected for analysis of immune cell gene expression profiles within the peripheral compartments will be evaluated for any relationship with efficacy endpoints. Serum samples may also be analyzed for analysis of circulating soluble factors in relation to immune status at baseline and in response to treatment. Factors to be analyzed may include but are not limited to IFN- $\gamma$ , tumor necrosis factor- $\alpha$ , interleukin (IL)-2, IL-6, IL-10, IL-8, IL-12, and levels of soluble PD-L1.

#### 9.3 Specimen Banking

If any tissue remains after analysis, it will be stored at the Tissue Bank at UT Southwestern for future research. Collaborators will be required to complete an agreement (a Material Transfer Agreement or recharge agreement) that states specimens will only be released for use in disclosed research. Any data obtained from the use of clinical specimen will be the property of UT Southwestern for publication and any licensing agreement will be strictly adhered to.

The specimens, DNA, and their derivatives may have significant therapeutic or commercial value. The Informed Consent form contains this information and informs the subject that there is the potential for financial gain by UT Southwestern, the investigator or a collaborating researcher or entity.

The following information obtained from the subject's medical record may be provided to research collaborators when specimens are made available:

- Diagnosis
- Collection time in relation to study treatment
- Clinical outcome if available
- Demographic data

#### 10.0 STATISTICAL CONSIDERATIONS

#### 10.1 Study Design/Study Endpoints

- 10.1.1 Study design: The study is a single armed, phase II trial to evaluate concurrent Durvalumab and radiotherapy followed by consolidative Durvalumab for Stage III Non-Small Cell Lung Cancer (NSCLC).
- 10.1.2 Primary endpoint of 12-month progression-free survival (PFS) rate is based on an assessment by an investigators according to RECIST 1.1 criteria; PFS is defined as the time from the study enrollment to documented progressive disease or death due to any cause, whichever occurs first;
- 10.1.3 Secondary endpoint of safety and tolerability will be assessed by adverse event according to CTCAE V.5;
- 10.1.4 Secondary endpoint of overall survival is defined as the time from study enrollment to death due to any cause;
- 10.1.5 Secondary endpoint of distant metastases free survival is defined as the time from the study enrollment to any new distant lesion:

- 10.1.6 Secondary endpoint of local and regional control defined as the time from the study enrollment to any local and regional lesion:
- 10.1.7 Exploratory endpoint of biomarker and biomarker correlatives;
- 10.1.8 Exploratory endpoint of proportion of patients alive at 12 and 24 months.

#### 10.2 Accrual

In the PACIFIC trial, patients who received consolidative durvalumab after chemoradiation had a 12-month PFS rate of 55%. PFS was measured starting after completion of chemoradiation, when anti-PDL1 treatment was started. This represents the assumed performance of the experimental arm in this study. We recognize that all patients who were randomized in the PACIFIC trial had tolerated and not progressed on chemoradiation, which represents some degree of selection bias. The possibility of early progression or treatment intolerance were taken into account when selecting the margins for the non-inferiority design of this study. A sample size of 47 achieves 80% power to detect a non-inferiority against an upper hazard ratio of 1.4 using a log-rank test at a 0.1 significance level when the actual hazard ratio is 1.0 and the standard of care group hazard rate is 0.5978 (which is equal to 1-year PFS rate of 55% using an exponential model). Three additional patients will be enrolled (total N=50) to account for 5% loss to follow-up. Patients will be accrued for a period of 3 years with 1-year follow-up.

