#### 1.4 Rationale

This study is designed to determine if adding durvalumab both during and after thoracic radiation for locally advanced NSCLC provides comparable outcomes to concurrent chemoradiation followed by consolidation durvalumab. Additionally, we hypothesize that the regimen under study will be better tolerated.

The benefit seen in PACIFIC, along with the growing role of immunotherapy for the treatment advanced (stage IV) NSCLC, suggests that earlier exposure to durvalumab may improve outcomes and be well tolerated, thereby permitting de-escalation of therapy through removal of conventional chemotherapy from these regimens. Indeed, the resulting improved outcomes from adding durvalumab to chemoradiation in the PACIFIC trial represent a greater magnitude of benefit from immunotherapy than was achieved from adding chemotherapy to thoracic radiation therapy. EORTC08844 compared radiotherapy alone, concurrent radiotherapy plus weekly low dose cisplatin and concurrent radiotherapy plus daily cisplatin (Schaake-Koning et al., 1992) showed improved overall survival rate of 12% with radiotherapy alone, 19% with weekly cisplatin and 26% with daily cisplatin. Another study showed similar improvement with the addition of carboplatin and VP16 (Jeremic, Shibamoto, Acimovic, & Djuric, 1995). They also represent a greater degree of benefit than has been observed from the addition of immunotherapy to chemotherapy in advanced NSCLC. Recently, IMpower131 trial enrolled 1,021 patients with stage IV squamous NSCLC randomly assigned to either atezolizumab plus carboplatin and nab-paclitaxel or carboplatin and paclitaxel alone. The median progression free survival is 6.3 months for atezolizumab plus chemotherapy compared to 5.6 months for chemotherapy alone (P=0.001) (Robert M. Jotte, 2018). Together, these observations suggest that thoracic radiation therapy and durvalumab represent a particularly favorable combination, supporting years of preclinical studies and case reports demonstrating synergy between radiation therapy and immunotherapy. PACIFIC2 and other ongoing trials provide evidence that concurrent thoracic radiation therapy and immune checkpoint inhibitor therapy is likely to be well tolerated. For example, concurrent palliative radiotherapy with durvalumab was well-tolerated in a cohort of patients included in a phase ½ trial in France (Levy, Massard, Soria, & Deutsch, 2016).

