# 2.0 STUDY OBJECTIVES

# 2.1 Primary Objectives

2.1.1 To determine the 12-month progression-free survival (PFS) rate for Stage III non-small lung cancer patients treated with concurrent durvalumab and radiotherapy followed by consolidative durvalumab;

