#### 10.3 Data Analyses

#### 10.3.1 Survival outcome

Progression-free survival and overall survival will be estimated using the Kaplan-Meier approach and the corresponding confidence intervals will be estimated using Greenwood's formula. Distant metastases-free survival, local and regional control will be estimated using the Kaplan-Meier approach.

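### The 80% power in section 10.2 belongs to a full-follow-up log-rank test, not to the 12-month PFS rate that is the primary endpoint; carried to month 12, the same margin gives about 61–64% at N=50

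*Combined protocol and SAP*

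**What the plan says.** Three parts of the combined protocol and SAP bear on the primary question.

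- **Endpoint.** Section 2.1 sets the objective: "To determine the 12-month progression-free survival (PFS) rate for Stage III non-small lung cancer patients treated with concurrent durvalumab and radiotherapy". Sections 2.4.1 and 10.1.2 agree: "Primary endpoint of 12-month progression-free survival (PFS) rate is based on an assessment by an investigators according to RECIST 1.1 criteria". The Study Summary names the same quantity.
- **Sample size.** Section 10.2 sizes the trial on a hazard ratio: "A sample size of 47 achieves 80% power to detect a non-inferiority against an upper hazard ratio of 1.4 using a log-rank test". The conditions follow: "using a log-rank test at a 0.1 significance level when the actual hazard ratio is 1.0", with a reference hazard of 0.5978 per year, equivalent to 55% PFS at one year under an exponential model. Three patients are added for 5% loss, giving 50. On timing: "Patients will be accrued for a period of 3 years with 1-year follow-up".
- **Analysis.** Section 10.3.1, and the Study Summary in the same terms, says: "Progression-free survival and overall survival will be estimated using the Kaplan-Meier approach and the corresponding confidence intervals will be estimated using Greenwood's formula". Neither mentions the log-rank test, the reference value, the 1.4 margin, the 0.1 level or a confidence level.

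Section 10.1.1 confirms that there is no concurrent control: "The study is a single armed, phase II trial". Section 1.4 gives the aim as learning whether the regimen "provides comparable outcomes to concurrent chemoradiation followed by consolidation durvalumab", and 10.2 itself describes a non-inferiority design.

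**The concern.** A power figure belongs to a particular test of a particular quantity. Section 10.2 attaches 80% to a test of the hazard ratio. The endpoint is a proportion at one time point, and the analysis section plans to estimate it without saying what result would count as non-inferior.

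A log-rank test over one to four years of follow-up uses events after month 12. A 12-month rate does not. If a large share of the expected events comes after month 12, the log-rank power cannot be read across to the rate.

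Two things are at stake. A reader of 10.2 would think that the primary endpoint has an 80% chance of showing non-inferiority when the regimen equals the reference. And in a single-arm study, a decision rule fixed in advance is the main protection against choosing the analysis after the data are seen.

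**Working it through.** **Inputs from section 10.2:** reference hazard 0.5978 per year (check: −ln 0.55 = 0.5978); margin HR 1.4; true HR 1.0; level 0.1; power 80%; accrual 3 years plus 1 year of follow-up; N=47, raised to 50 for 5% loss. **Assumed:** uniform accrual.

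**1. Reproduce N=47.** With hazard λ, the probability of an event during the study is 1 − [e^(−λ) − e^(−4λ)]/(3λ).

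- At HR 1.0 it is 0.744, so 47 × 0.744 = 35.0 events.
- At HR 1.4 it is 0.842.

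Two one-sample log-rank formulas at one-sided 0.10 arrive at the stated figure:

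- (O−E)/√E form: E = [(1.2816 + 0.8416·√(1/1.4))/(1 − 1/1.4)]² = 48.65; observed events 48.65/1.4 = 34.75; N = 34.75/0.744 = 46.7.
- Log hazard ratio form: (1.2816 + 0.8416)²/(ln 1.4)² = 39.8 events; N = 39.8/0.842 = 47.3.

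So the sponsor's exact formula is not established, but the type of test is: one-sample, one-sided, all follow-up. At two-sided 0.10 the same two formulas need 65.3 and 64.9. Two-sample formulas need about 160 events. Cutting follow-up at 12 months raises the requirement to 70–88 patients. Simulated power of the full-follow-up test is 76–78% at n=47 and 79–80% at n=50, if the exponential reference is true.

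**2. Share of that information available at month 12.** By month 12, 47 × 0.45 = 21.2 of the 35.0 expected events have occurred. The other 14 or so help the log-rank test but not the 12-month rate.

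**3. Power for the 12-month rate.** The documents give no margin on this scale. Carrying HR 1.4 to month 12 under the protocol's exponential model gives 0.55^1.4 = 0.433. The assumed rule is that the one-sided 90% lower limit must exceed 43.3%. With everyone known at month 12, the untransformed Greenwood limit is p − 1.2816·√(p(1−p)/n), and exact binomial probabilities apply.

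- n=50: 26/50 gives a limit of 0.4295 (fail) and 27/50 gives 0.4497 (pass). Power at 55% is 61.3%; actual alpha at 43.3% is 0.084. The log-log and logit scales have the same pass mark. The log scale passes at 26/50, with alpha 0.136.
- n=50 with 5% loss by month 12 (assumed exponential), simulated Kaplan-Meier with Greenwood: power about 64%, alpha about 0.097.
- n=47: the rule passes at 25/47 with power 65.5%, but alpha is 0.111. The smallest mark that holds alpha to 0.10 is 26/47, with power 54.3%.
- The unstated confidence level matters. At n=50, untransformed, a two-sided 90% interval passes at 28/50 (power 50.2%) and a two-sided 95% interval at 29/50 (39.0%).

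**4. Could the log-rank test simply be made primary?** A constant hazard of 0.5978 implies a median of 12 × ln 2/0.5978 = 13.9 months. Section 1.1 gives 17.2 months for the PACIFIC durvalumab arm. At 17.2 months the exponential predicts e^(−0.5978 × 17.2/12) = 42.4%, where the median requires 50%. A curve through 55% at 12 months and 50% at 17.2 months has a hazard of ln(0.55/0.50)/(5.2/12) = 0.22 per year between those points. Simulate a regimen with 1.4 times the hazard of that curve at all times, and test it at n=50 against the constant-hazard reference. It passes in about 25–27% of trials if the later reference hazard returns to 0.5978, and in 68–70% if it stays at 0.22. The nominal rate is 10%. The hazard after 17.2 months is assumed.

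**The case against.** The best defence is that 10.2 contains the only inferential rule in the documents and that 10.3.1 merely describes estimation. On that view the log-rank test is the primary analysis by implication, the 80% is roughly right for it, and only a cross-reference is missing. Non-inferiority against an upper hazard ratio is also naturally one-sided. Part of this stands: the arithmetic in 10.2 is sound for the test it names, and no rival decision rule is written anywhere. But a sample-size sentence does not displace an endpoint defined as a 12-month rate in sections 2.1, 2.4.1 and 10.1.2, and the implied test would depend on the extrapolation shown to be doubtful in step 4.

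A second objection is that the 43.3% threshold and the 90% limit are not in the protocol. That is correct. The mismatch does not depend on them, but every 12-month power figure does.

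Two stronger readings should be resisted. A reader might infer that the two analyses would often give opposite verdicts. Simulation at true HR 1.0 does show disagreement in about 20–23% of trials, but that sets the protocol's test against an assumed rule, so the documents alone do not establish it. A reader might also infer that naming the log-rank test in 10.3.1 would let the 80% stand. That holds only if the exponential reference is right beyond month 12. The quoted median of 17.2 months carries a 95% interval of 13.1 to 23.9, so 13.9 months is not excluded, but the protocol's point figures do not support it.

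**Conclusion.** The point holds. The 80% in 10.2 is a property of a one-sample, one-sided log-rank test over all follow-up, and it does not apply to the endpoint the protocol calls primary. For the 12-month rate, with the margin carried over as above, power at N=50 is about 61–64%, or 16 to 19 points lower. This rests on the exponential translation of the margin, a one-sided 90% lower limit and an untransformed scale; a stricter interval would lower it further.

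Strictly, as 10.3.1 stands, no power figure attaches to the planned analysis, because it contains no test. The finding is not that N=47 was miscalculated or that the trial cannot be run with 50 patients. It is that the stated power and the stated endpoint do not belong together and that the decision rule is unwritten. It should be fixed before analysis.

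**What to change.** Keep the 12-month PFS rate as the deciding analysis.

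- **10.3.1:** state that non-inferiority is concluded if the one-sided 90% lower Greenwood limit for 12-month PFS exceeds 43.3%, and name the scale. The untransformed scale matches the figures given here; the log scale would exceed the 0.10 level at n=50.
- **10.2:** say that the 0.1 level is one-sided, give the 43.3% threshold and its derivation from HR 1.4, and replace 80% with about 61–64% at N=50.
- **Study Summary:** align the statistical methodology entry.

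Do not make the full-follow-up log-rank test against a constant 0.5978 the deciding analysis. If the sponsor prefers a log-rank test, either cut it at 12 months or use a reference curve that matches the PACIFIC figures in the protocol, and restate its power. Cut at 12 months, the constant-hazard version has about 60–68% power at n=47.

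**Cost:** changes to the text, made as an amendment with IRB approval under section 11.6, and a less favourable stated power. No extra patients are needed. Keeping 80% for the 12-month rate would instead take about 82 patients (untransformed: (1.2816 + 0.8416)² × 0.55 × 0.45/0.117² ≈ 82) to 92 (log-log).

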#### 1.0 BACKGROUND AND RATIONALE

### 1.1 Disease Background

Until the recent developments of immunotherapy, we have reached a plateau in outcomes for locally advanced non-small cell lung cancer (LA-NSCLC). Despite aggressive therapy with concurrent chemoradiation, fewer than 20-25% of patients with stage III NSCLC achieve 5-year survival and are presumably cured. To date, modifications of chemotherapy or dose escalation of radiotherapy (RT) have not improved these outcomes.

Immunotherapy has significantly improved the survival outcomes of patients with various cancer types including thoracic malignancies. In the PACIFIC study, patients with locally advanced NSCLC were randomized to the anti-PDL1 antibody durvalumab or placebo for up to 12 months after completion of concurrent chemoradiation. Outcomes in the durvalumab arm were significantly better, regardless of tumor PDL1 status. Median PFS was 17.2 months in the durvalumab group (95% CI, 13.1 to 23.9) vs. 5.6 months (95% CI, 4.6 to 7.7) in the placebo group. The 24-month overall survival rate was 66.3% (95% confidence interval [CI], 61.7 to 70.4) in the durvalumab group vs. 55.6% (95% CI, 48.9 to 61.8) in the placebo group (two-sided P=0.005). (Antonia et al., 2018; Antonia et al., 2017). The time to death or distant metastasis was longer in the durvalumab group than in the placebo group (median, 28.3 months [95% CI, 24.0 to 34.9] vs. 16.2 months [95% CI, 12.5 to 21.1]; stratified hazard ratio, 0.53; 95% CI, 0.41 to 0.68). Following this study, consolidation durvalumab after chemoradiation received FDA approval and is now considered standard of care.

While NSCLC is typically considered relatively non-immunogenic, RT is thought to augment tumor immunogenicity(Iyengar & Gerber, 2013). The abscopal effect refers to the observation that RT to a local area results in an antitumor effect distant to the radiation site. One proposed mechanism for this phenomenon is inducing the release of circulating tumor antigen or inflammatory factors that could then mediate an augmented immune response against distant malignant lesions expressing similar tumor antigens. Supporting this hypothesis, local RT has been shown to increase the activity of natural killer cells (Uchida, Mizutani, Nagamuta, & Ikenaga, 1989).

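### The constant reference hazard in section 10.2 does not fit the PACIFIC median in section 1.1, so a log-rank comparison using follow-up beyond month 12 would be too lenient at the cited point estimates

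*Combined protocol and SAP*

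**What the plan says.** Section 10.2 takes its benchmark from one PACIFIC figure: "patients who received consolidative durvalumab after chemoradiation had a 12-month PFS rate of 55" per cent. It converts this to a constant yearly hazard, stating that "the standard of care group hazard rate is 0.5978 (which is equal to 1-year PFS rate of 55% using an exponential model". The design sentence reads "A sample size of 47 achieves 80% power to detect a non-inferiority against an upper hazard ratio of 1.4". The test it names is a log-rank at level 0.1, and it takes the true hazard ratio as 1.0. On timing, "Patients will be accrued for a period of 3 years with 1-year follow-up", so a patient is observed for between 1 and 4 years.

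Section 1.1 gives a second figure for the same PACIFIC arm: "Median PFS was 17.2 months in the durvalumab group (95% CI, 13.1 to 23.9" months).

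The primary endpoint (sections 2.4.1 and 10.1.2) is the 12-month PFS rate. Section 10.3.1 plans Kaplan-Meier estimates with Greenwood intervals. It names no test, comparator curve or decision rule.

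**The concern.** With no control arm, a one-sample log-rank test compares the observed events with the number expected under a reference hazard. The only reference hazard in the protocol is the exponential in 10.2, which is anchored at month 12 and extrapolated beyond it. If that curve progresses faster than the PACIFIC arm did after month 12, expected events are too many and non-inferiority becomes easier to declare. Section 1.4 asks whether outcomes are comparable to chemoradiation followed by consolidation durvalumab, so a lenient reference would weaken the answer to the trial's main question.

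**Working it through.** **Inputs.** From 10.2: 55% PFS at 12 months, hazard 0.5978 per year, margin 1.4, true hazard ratio 1.0, level 0.1, power 80%, N=47, 3 years of accrual plus 1 year. From 1.1: median 17.2 months (95% CI 13.1 to 23.9). Assumptions: uniform accrual and a one-sided level. Section 10.2 does not give the sidedness, but one-sided reproduces its N.

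**1. The plan's own figure.**
- Hazard: λ = −ln(0.55) = 0.5978 per year.
- Event probability with all follow-up: p = 1 − (e^(−λ) − e^(−4λ))/(3λ) = 1 − (0.5500 − 0.0915)/1.7935 = 0.744.
- One-sample log-rank with Poisson variances: n = (z₀.₉₀√1.4 + z₀.₈₀)²/(0.4² p) = (1.2816 × 1.1832 + 0.8416)²/(0.16 × 0.744) = 5.560/0.1191 = 46.7, rounded up to 47. Dividing by 0.95 gives 50.
- With follow-up cut at month 12, p = 0.45 and the same formula gives 77.2.
- So N=47 needs later events. Of 47 × 0.744 = 35 expected events, a share 1 − 0.45/0.744 = 0.395, or about 14, falls after month 12.

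**2. The two PACIFIC figures together.**
- Median of the stated exponential: 12 × ln 2/0.5978 = 13.9 months.
- Its PFS at 17.2 months: exp(−0.5978 × 17.2/12) = 42.4%, against 50% by the reported median.
- An exponential with median 17.2 months has hazard ln 2/(17.2/12) = 0.484 and 12-month PFS e^(−0.484) = 61.7%, not 55%.
- Hazard between months 12 and 17.2 if both points hold: ln(0.55/0.50)/(5.2/12) = 0.220 per year. The planned value is 2.7 times that.

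**3. Effect on the error rate.** Simulation with N=47 and 40,000 to 60,000 trials per scenario. The true hazard ratio is 1.4 against a curve through both PACIFIC points. The test uses the 0.5978 exponential: E is 1.4 times the summed reference cumulative hazard, and non-inferiority is declared if (O − E)/√E < −1.2816. The documents do not give the hazard after 17.2 months in figures, so it is varied.

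| Assumed hazard after 17.2 months | False non-inferiority, exponential reference | Same, follow-up cut at month 12 | Power at N=47 with the matching reference |
|---|---|---|---|
| 0.22 | about 66% | 9% | about 71% |
| 0.40 | about 44% | 9% | about 73% |
| 0.5978 | about 25% | 9% | about 75% |

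When the exponential is itself the truth, the same simulation gives an error of 9% and power of about 76%. The cut at month 12 restores the level in every row, so the cause is the shape after month 12.

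**4. Uncertainty in the median.** With 55% at month 12 held fixed and a constant hazard after it, error at a true hazard ratio of 1.4 is:
- median 13.1 months (later hazard 1.04): about 0.2%
- median 17.2 months (0.22): about 66%
- median 23.9 months (0.096): about 88%

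**5. Power if the comparison stops at month 12.** Simulated power is about 62% at N=47 and 64% at N=50.

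**The case against.** The strongest reply is that the log-rank test appears only in the sample-size sentence. The endpoint is a 12-month rate and 10.3.1 plans Kaplan-Meier estimation. A 12-month Kaplan-Meier rate set against 55% does not depend on the curve after month 12. This stands. A reader might infer that the trial's 0.1 level fails outright. The documents do not support that, because they never say which analysis decides non-inferiority. The inflated error applies only if the test in 10.2 does. The reply does not rescue 10.2, though: if the decision is taken at month 12, the stated power for N=47 no longer applies.

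Second, 13.9 months lies inside the published interval of 13.1 to 23.9, so the conflict is between point estimates. This also stands, and it limits what can be said about size. It does not justify the choice of curve: 10.2 adopts a PACIFIC point estimate as its benchmark, and 13.9 is near the lower, lenient end of the interval.

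Third, 10.2 says its margin allows for early progression and treatment intolerance. That concerns patient selection, not the hazard after month 12.

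A reader might also divide the margin hazard, 1.4 × 0.5978 = 0.837, by 0.484 and report an effective margin of 1.73. That figure should not be used. It rests on an exponential with 61.7% PFS at month 12, which contradicts the 55% benchmark.

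**Conclusion.** The point holds conditionally. The constant hazard in 10.2 and the median in 1.1 cannot both describe the PACIFIC arm through a single exponential, and N=47 depends on the part of the curve where they disagree. If the log-rank comparison is primary, its reference is too lenient after month 12 at the cited point estimates, with false non-inferiority of about 25 to 66% against a nominal 10%.

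That range treats 55% and 17.2 months as exact and varies only the hazard after 17.2 months. Carrying the median's interval through widens it to about 0.2 to 88%, so the direction follows from the point estimates but the size is not established. The different time origins (enrollment here, the end of chemoradiation in PACIFIC) are a separate matter that 10.2 partly acknowledges, and these figures do not address them. Severity: should-fix.

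**What to change.** State in 10.2 and 10.3.1 which comparison decides non-inferiority.

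- **If it uses all follow-up:** replace the single exponential with a reference cumulative hazard that matches both cited PACIFIC figures. This can be the Figure 1B curve, or a piecewise exponential of 0.5978 to month 12 and about 0.22 to month 17.2, with the later hazard stated as an assumption and varied. Compute expected events from it and restate power at N=47 as about 71 to 75%. Keeping 80% by the formula in step 1 would take about 50 evaluable patients if the hazard returns to 0.5978 after 17.2 months (34.75/0.706 = 49.2), or 59 if it stays at 0.22 (34.75/0.597 = 58.2), where 34.75 = 5.560/0.16.
- **If it is restricted to 12 months:** the 55% benchmark can stay, but restate power as about 62% at N=47 (64% at N=50). Keeping 80% by the formula would take about 78 evaluable patients.

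Either route needs only wording and a recalculation if the lower power is accepted. No new data items are needed.
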